	teen mobile unit. Participants will be invited to come to the Desmond Tutu HIV Foundation satellite research site in Philippi village for consent procedures, medical study components and group sessions.
Study drugs	Oral Pre-exposure prophylaxis (Truvada) (one month supply); STI treatment: N. gonorrhoea – Ceftriaxone 250 mg injection (Rocephin®) AND Azithromycin (Zithromax™) 1g orally; C. trachomatis – Azithromycin (Zithromax™) 1g orally; T. vaginalis – Metronidazole (Flagyl™) 2g orally; HIV testing and counseling (HTC)
Study population	15 – 19-year-olds, AGYW and their Female Caregivers (24 years and older)
Sample size	A total of ~1250 participants are expected to be enrolled across all study components as follows: 
 1. Up to 96 participants in aim 1 theatre testing component 2. Up to 100 participants in the pilot study 3. Up to 1050 participants in the RCT 4. Up to 40 participants in the qualitative component
Treatment regimen	Referral to ART clinics for HIV positive participants; Referral for PrEP for HIV negative participants with a one month supply provided at enrolment if participants are willing to take PrEP.
Study duration	5 years (2 years UG3 feasibility) and (3 years UH3 RCT)
Duration of enrolment and accrual	36 months
Primary endpoints	An adapted and tailored SA IMARA curriculum; Impact of IMARA on HIV and STI incidences; PrEP uptake; HTC uptake; Cost effectiveness and scalability of IMARA; Sexual risk behaviour (condom use, number of partners)
Key secondary endpoints	AGYW-FC relationship (warmth, acceptance, monitoring, permissiveness); AGYW-FC communication (quality, frequency); HIV knowledge (HIV/STI transmission, prevention); HIV-related Stigma; HIV and STI attitudes; AGYW mental health (depression, anxiety, trauma); AGYW and FC knowledge, attitudes and beliefs about PrEP and HTC; Adherence (PrEP and ART); Gender roles and gender-based violence; Drug use; Partner communication; and Power relationship dynamics.

IMARA-1 Study Protocol

Protocol Title: Multilevel Comprehensive HIV Prevention Package for South African Adolescent Girls and Young Women

Protocol PI: [name]

Version 5.0: 14 May 2020

Approved 10JUN2019

Amendment approved xx-xxx-xxxx

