2. STUDY DESIGN

2.1 Study overview, study design, area and setting

The complete study will be conducted in two phases (**Table 2**). Phase 1 will adapt and evaluate feasibility of the IMARA program in preparation for a Randomized Control Trial (RCT) in phase 2. We request ethics approval for phase 1 of the study. A separate application for phase 2 will be submitted once phase 1 is complete. Therefore, the methods presented below focus on phase 1 of the study.

Table.2

IMARA-1 Study Protocol

Protocol Title: Multilevel Comprehensive HIV Prevention Package for South African Adolescent Girls and Young Women

Protocol PI: [name]

Version 5.0: 14 May 2020

Approved 10JUN2019

Amendment approved xx-xxx-xxxx

Phase 1 study methods (UG3)

A mixed methodology

1. Theatre testing (group discussions) and adapting the curriculum for SA youth n=48 (AGYW-FC dyad)
2. Pilot testing with approximately 50 AGYW-FC dyad to establish feasibility for the RCT in phase 2

Phase 2 study methods (UH3) (*separate Ethics application*)

A mixed methodology

1. RCT with AGYW-FC dyad n=525
2. Evaluate cost effectiveness
3. Interviews with (AGYW-FC dyad) n=40

Study area and Setting.

We will implement the study in the Klipfontein/ Mitchells Plain (K/MP) health sub-district of the Western Cape metropolitan area and neighbouring communities including Gugulethu, Crossroads and Philippi. Generally, the selected communities a high HIV/TB burdened, low resource, and high-density community. Recent data on 15-19 year-old females in the sub-district revealed high rates of incident STI (7.4%), STI prevalence (52%), intergenerational sex (20%), concurrent partners (27%) and low rates of condom use (42%).²⁰² Thus, this is an ideal setting for this study. We will also recruit participants from our Tutu Teen mobile unit (TTMU) which targets adolescents.

2.2 Study Participants and procedures for phase 1

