AGYW will report on their risk behavior and provide biological specimens for STI and HIV testing. **(1) HIV/STI Risk Behaviors.** *AIDS-Risk Behavior Assessment (ARBA)*²³⁶ is a computer-assisted structured interview of self-reported sexual behavior, drug use, and HIV status derived from 5 well-established measures,²³⁷⁻²⁴² and used extensively in published research. The ARBA employs a skip structure so that questions initially answered “no” are not followed by more detailed questions. We will use specific indicators (e.g., number of partners), frequency measures, count variables (e.g., number of unprotected sex acts), and composite scores to assess risky sex. We will also calculate lifetime sexual behavior and the ratio of protected to unprotected sex acts. The measure has been used with SA adolescents. **(2) PrEP uptake.** **(3) HIV and STI incidence.**

Data Reduction and Analyses.

We will generate frequencies and summary statistics of predictor and outcome variables to screen and clean the data. We will check the success of randomization by comparing intervention groups on baseline variables using chi-square tests for categorical variables and t-tests or nonparametric Wilcoxon rank-sum tests for continuous variables. In subsequent analyses, we will control for predictor variables that are not balanced across arms at baseline. We also will check for differences between AGYW in IMARA-SA and FUEL-SA in subsequent analyses. We will create summary scores for AGYW on the following variables: (1) sexual activity, HIV and STI incidence, PrEP and HTC uptake; (2) individual drivers (mental health/emotion regulation; HIV/AIDS knowledge, attitudes, beliefs, skills; PrEP and HTC attitudes and beliefs); (3) sociocultural drivers (partner concurrency; family context); and (4) structural drivers (gender dynamics; HIV/AIDS stigma). We will conduct analyses on individual outcome indicators and on composite scores comprised of multiple indicators for the pilot study in aim 2.

Participant reimbursement

Participants will not be paid to participate in the intervention, but they will be reimbursed for their time and transport: AGYW and FC will each receive R120 for the theater test and R130 for the pilot test at each study visit.

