3. HUMAN SUBJECTS PROTECTION

All human subject procedures conform to the recommendations Procedures follow the “Ethics in Health Research: Principles, Processes and Structures – 2015” guidelines, as mandated

IMARA-1 Study Protocol

Protocol Title: Multilevel Comprehensive HIV Prevention Package for South African Adolescent Girls and Young Women
Protocol PI: [name]

Version 5.0: 14 May 2020

Approved 10JUN2019

Amendment approved xx-xxx-xxxx

by the South African National Health Research Ethics Council. This application proposes to conduct phase 1 of the study which will adapt the intervention curriculum and pilot test all procedures that will be conducted in phase 2 RCT. During phase 1, we will first conduct theater testing with 48 AGYW/FC dyads and then pilot test the feasibility of the intervention with approximately 50 additional dyads. Inclusion and exclusion criteria. AGYW will be: a) black or mixed race; b) 15-19 years-old; c) residing in K/MP; and d) speak isiXhosa, English or a combination as these are the primary regional languages. AGYW may or may not be sexually active and information about their sexual activity will not be shared with caregivers, reducing consent/assent barriers. FC will be: a) selected by the AGYW and agreed upon by the mother/caregiver; b) 24 years and older; c) living with or in daily contact with the AGYW; and d) speak similar languages. FC and AGYW must agree to participate as a dyad, but AGYW refusal will supersede caregiver consent. We will include HIV-infected and uninfected FC and AGYW. AGYW and FC will be excluded if they: a) are unable to understand the consent/assent process; and b) do not speak English, isiXhosa because instruments are normed for these languages. AGYW will be excluded if they do not have a FC. Participants in phase 1 (theater testing, pilot test) will be excluded from phase 2. If there is more than 1 eligible AGYW in a family, we will randomly select 1 to maintain independent observations. If AGYW or FC become pregnant during the course of the study, they may remain enrolled in the study. We will link participants who become pregnant over the course of the study to prenatal care. Our trained staff will provide these services or refer participants to appropriate clinics.

3.1: Informed Consent

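### The planned ratio of protected to unprotected sex acts cannot score AGYW whose acts were all protected; the proportion protected can, but AGYW with no acts still need their own rule (minor)

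*Combined protocol and SAP*

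**What the plan says.** The measure appears once, under Expected outcomes, in the paragraph on HIV/STI risk behaviours taken from the ARBA interview: "We will also calculate lifetime sexual behavior and the ratio of protected to unprotected sex acts". The same paragraph also plans "count variables (e.g., number of unprotected sex acts), and composite scores to assess risky sex", together with indicators such as number of partners and frequency measures. It notes that the ARBA skips detailed questions after an initial no, without saying how skipped items are scored.

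Data Reduction and Analyses adds that indicators will be analysed singly and within composites, but gives no composite formula. It names t-tests and Wilcoxon tests only for checking baseline balance.

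Section 3, Human Subjects Protection, states of eligibility that "AGYW may or may not be sexually active". The Protocol Summary lists condom use within sexual risk behaviour under primary endpoints and expects condom use to rise under IMARA-SA. No section says which variable measures it.

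**The concern.** A ratio whose denominator is the number of unprotected acts fails where the intervention succeeds most. An AGYW who moves from sometimes to always using condoms goes from a finite score to none. An AGYW with a single act can score only 0 (unprotected) or nothing (protected). An AGYW with no acts gives 0/0.

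If software or an analyst sets these values to missing, the loss depends on outcome. It would be larger in whichever arm has more consistent users, and the remaining comparison would describe inconsistent users only. A composite containing the ratio could inherit the gap.

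**Working it through.** **Inputs.** P = protected acts and U = unprotected acts per AGYW. About 50 AGYW, about 25 per arm (Aim 2, Randomization). Local condom use of 42% (section 2.1, Study area and Setting), not defined as per act, last sex or consistent use. The documents attach no sample size, power or alpha to this measure, so there is no figure of the plan's own to reproduce.

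**Step 1: boundary cases.** Ratio = P/U; proportion = P/(P+U); count = U.

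| P, U | Ratio | Proportion | Count of unprotected acts |
|---|---|---|---|
| 0, 10 | 0 | 0 | 10 |
| 1, 9 | 0.11 | 0.10 | 9 |
| 5, 5 | 1 | 0.50 | 5 |
| 9, 1 | 9 | 0.90 | 1 |
| 10, 0 | undefined | 1 | 0 |
| 1, 0 | undefined | 1 | 0 |
| 0, 0 | undefined | undefined | 0, if skips are coded 0 |

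The proportion repairs the all-protected rows but not the last one. Only the count has a value in every row.

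**Step 2: how many of 50.** Let a be the share with no acts and c the share of active AGYW whose acts were all protected. Neither is in the documents; assume a = 20 to 60% and c = 10 to 42%.
- Ratio undefined: 50a + 50(1 − a)c. Lowest 10 + 40 × 0.10 = 14; highest 30 + 20 × 0.42 = 38.4.
- Proportion undefined: 50a = 10 to 30.
- Difference, due to the all-protected case alone: 50(1 − a)c, from 20 × 0.10 = 2 to 40 × 0.42 = 16.8.

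**Step 3: what dropping does.** Take three AGYW at (1, 9), (5, 5) and (9, 1). Mean ratio = (0.11 + 1 + 9)/3 = 3.37; mean proportion = 0.50. Let one become (10, 0) and drop her ratio.
- The highest user converts: mean ratio (0.11 + 1)/2 = 0.56; mean proportion (0.10 + 0.50 + 1)/3 = 0.53.
- The middle user converts: (0.11 + 9)/2 = 4.56; proportion (0.10 + 1 + 0.90)/3 = 0.67.
- The lowest user converts: (1 + 9)/2 = 5; proportion (1 + 0.50 + 0.90)/3 = 0.80.

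Averaged over who converts, the ratio is (0.56 + 4.56 + 5)/3 = 3.37, its starting value. Random conversion is therefore invisible on average, while preferential conversion of high users points the wrong way. The proportion rises each time.

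**Step 4: simulation under stated assumptions.** Undefined values dropped; every AGYW active and retained; 10 acts each; two-sided Wilcoxon at 5%. Reading A: 42% are always-users, the rest follow Beta(2,3), and 18/58 of inconsistent users convert to always-use. Reading B: 42% is mean use (3% always-users plus Beta(2,3), or Beta(2.1,2.9) alone) and 10 or 18.6% convert. The size is 525/2, about 262 per arm, which is the phase 2 size and not the pilot's.

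| Response pattern | Ratio, undefined dropped | Proportion |
|---|---|---|
| Random conversion, no other change | A and B: 5% (chance, both directions) | A 97%; B 48–97% |
| Conversion, and others improve too | A 40–88%; B 66–99% | A and B: 99% or more |
| Higher users convert preferentially | favours control: A 30%; B 6–15% (chance 2.5%) | correct: A 90%; B 33–81% |
| Inconsistent users improve, no conversion | A 93%; B about 99% | A 39%; B about 99% |

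Undefined shares, control against IMARA, are 43% against 60% under A and about 1–4% against 11–23% under B, in the patterns with conversion. At 25 per arm, power over these patterns is 1–27% for the ratio and 7–61% for the proportion.

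**The case against.** The strongest reply is that the harm comes from dropping values, which no section says will happen. The ratio equals p/(1 − p), where p is the proportion, so it is a monotone transform. If all-protected AGYW are ranked highest, the two measures order active AGYW identically and a Wilcoxon test gives the same result. This stands. It makes the power figures conditional, and it means that a one-line scoring rule would serve a rank test. It does not give the ratio a mean for all-protected AGYW, whereas the proportion supplies one from the same items.

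A reader might infer that the proportion cures both undefined cases. It does not: no acts gives 0/0 there too. Restricting to AGYW with acts at follow-up also conditions on behaviour after randomisation. Section 1.1 links open mother-daughter communication to reduced sexual experience, so IMARA could change who is left in. This objection stands and shapes the remedy.

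A reader might also infer that the RCT's condom-use result is at risk. The documents do not support that. Section 3 says this application will "pilot test all procedures that will be conducted in phase 2 RCT", but section 2.1 says "A separate application for phase 2 will be submitted once phase 1 is complete", so reuse of the ratio is hypothetical. The 262-per-arm figures also assume that everyone is active and retained. With 60% active (assumed) and 80% retained (the milestone level), about 262 × 0.6 × 0.8 = 126 per arm would contribute.

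Finally, the survey appendix and the ARBA scoring instructions are not in the supplied text. The absence of a rule can be claimed only for these documents.

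**Conclusion.** The point holds, at minor severity. By arithmetic, the planned ratio has no finite value for AGYW whose acts were all protected, and the supplied documents give no rule for scoring them. If such values were treated as missing, consistent condom users would leave the measure, more often in the better arm, and a benefit could be weakened or hidden. How much depends on the undefined 42%, the number of acts, who changes behaviour, and the unstated handling of undefined values. Under reading B, if use rises without conversion to always-use, there is no harm.

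A claim that the ratio will hide or reverse IMARA's effect would go too far; so would treating it as the primary condom-use variable, since no section names it as such. It is one of several pilot indicators, the count of unprotected acts is unaffected by the all-protected case, no transition milestone depends on condom use, and about 25 per arm is not decisive on any of these measures.

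**What to change.** In the Expected outcomes paragraph on risk behaviours:

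1. Replace the ratio with protected/(protected + unprotected), among AGYW with at least one act in a stated recall period. All-protected AGYW then score 1.
2. Report by arm the number of AGYW with no acts in that period.
3. Use the already planned count of unprotected acts in all randomised AGYW, scored 0 for those who report no sex (including those skipped by the ARBA), as the comparison that keeps the randomised groups intact.

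**Cost.** Analysis wording only; the ARBA items do not change. The proportion is conditional on sexual activity after randomisation, so it should be read as descriptive beside the count. It can be less sensitive when many AGYW are already always-users, because they stay in and cannot improve (39% against 93% in the last row of the simulation, reading A). The count reflects how often AGYW have sex as well as condom use, so it merges abstinence with protection.

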a) Aim 2: Pilot testing with ~50 AGYW-FC dyads (~100 total participants) to establish acceptability and feasibility in preparation for the RCT in phase 2
Recruitment, enrolment and procedures for AIM 2

We will pilot test the revised IMARA curriculum with ~50 new AGYW-FC dyads, using the same eligibility and recruitment procedures described above. Groups will include approximately 6-8 dyads and participants will be followed for 12 months. The procedures for aim 2 are described next:

- We will schedule 8-10 dyads in each cohort to comprise one group. Upon arrival at the research site (Philippi village), trained staff will review consent and assent documents, ensuring comprehension and evaluating if participants are willing to participate.
- Following the consent/assent process, all AGYW and FC will complete a baseline assessment via computer-assisted self-interview (approx. 1 ½ hours) and indicate their desire to test for HIV and STIs and willingness to take PrEP. If willing to test for HIV and STIs, both AGYW and their FC will receive HIV/STI counselling and testing. AGYW and FC have the option to refuse testing and still remain in the study.
- Randomization (control vs. intervention): We will randomize participants to treatment arm upon completion of the baseline assessment so as not to lose families due to bias in advance. Approximately 25 dyads will be randomly assigned to the health promotion group and ~25 dyads to IMARA. Randomization will follow the fish-bowl method, where equal numbers of RED and WHITE cards will be placed in the fish bowl. AGYW will select a card. The two intervention groups will take place in different rooms. The control and IMARA curricula are matched for time and attention.
- The first group session (approx. 3 hours) will be delivered immediately following randomization. Participants will be at site for 6.5 hours for their first session activities, including the baseline assessment and intervention.
- Participants will return one week later for day 2 of the intervention.
- The total time of the intervention is approximately 12 hours.
- Participants who agreed to test for HIV will be given their results at the end of day 1. If HIV positive, referral for care in the regular public ART clinics will be provided. For those who agreed to test for STIs, results will be ready by session 2. If positive, the DTHF nurse will provide STI risk reduction counselling and treatment. We will request the partner be treated as well.

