- For participants who are HIV negative and opt to take PrEP in our baseline survey, we will provide a one month PrEP prescription with a referral to public, youth friendly clinics currently offering PrEP. We will draw blood for safety monitoring of creatinine in

IMARA-1 Study Protocol

Protocol Title: Multilevel Comprehensive HIV Prevention Package for South African Adolescent Girls and Young Women

Protocol PI: [name]

Version 5.0: 14 May 2020

Approved 10JUN2019

Amendment approved xx-xxx-xxxx

accordance with the national guidelines. We will additionally test blood draws for Hepatitis B, in line with national guidelines, among participants who opt to take PrEP at the 6- and 12-month follow-up points. Urine will be tested for pregnancy. Renal function (e.g., creatinine clearance, CrCl) will be tested and all results will be supervised by a medical member of our team. Participants will receive the results with referral documents for the next dose of PrEP.

- At each follow up data collection point and after the second session, we will re-invite individuals for HIV and STI testing. We will also re-invite participants to receive PrEP, unless they accepted PrEP from us at a previous data collection timepoint, were linked to care, and are receiving PrEP from a clinic. Should they be willing to test and to use PrEP, the same procedures as above will apply. At the end of their first month post PrEP initiation and referral, the team will follow up on PrEP and ART uptake at clinics including where they plan to seek PrEP or ART services. We will also ask about whether side effects participants are experiencing when they come for their second visit a week after the first session. We encourage all our participants to contact us should they experience any side effects once they have started using PrEP. During follow-up visits at 6- and 12- months, we will additionally use dried blood spots (DBS) to assess adherence to PrEP among those who have accepted PrEP.
- We will implement extensive retention and tracking procedures (see retention and tracking procedures section below).
- We will re-interview AGYW and FC 6- and 12-months after baseline for preliminary evidence of feasibility and acceptability, particularly with regard to the procedures for HTC, STI and PrEP uptake, and linkage to care for treatment.

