In addition to theatre testing and curriculum adaptation data collected verbally and through written notes, we will collect baseline data for the pilot using Qualtrics software on tablet computers. Participants will read the surveys on their own with the assistance of our trained data collection staff who are present to conduct the actual survey with participants if they are unable to read, or with the assistance of Audio Computer-Assisted Self Interview (ACASI). . A paper-based survey will be in hand and ready for use should we experience any challenges with the electronic versions. AGYW and FC (N=100 total) will be tested for three STI (chlamydia, gonorrhoea, trichomonas). A medical officer will arrange single dose antibacterial treatment for all participants who test positive for an STI. We will also offer HTC and HIV results to each participant. We will offer PrEP at the baseline assessment, and AGYW and FC who test negative for HIV and/or express a desire to take PrEP will be referred to a medical officer, who will facilitate care at the site.

The 6- and 12-month surveys may be administered either in person or via telephone. Participants may be asked only a subset of interview questions, depending on time and availability. Participants will also be asked a set of questions that were not included on the baseline survey about the COVID-19 virus. For surveys administered in person, data collection and clinical assessments will follow the same procedures as detailed above. For surveys administered via telephone, after obtaining consent/assent, study staff will ask participants each question and record their responses using Qualtrics software on tablet computers. Participants will be informed that they will be given the opportunity to complete HTC, STI, and/or PrEP clinical assessments when they are next on site.

Baseline survey Questionnaire (see Appendix B). Most of the measures have been used extensively with SA adolescents and caregivers and demonstrate acceptable psychometric properties in isiXhosa.

- a) **Participant Demographics.** For AGYW < 18 years old, we will ask caregivers to provide residential and e-mail addresses, home and cell phone numbers, and contact information for at least 3 people who can help us locate families in the future. We will also collect maternal age and education, family income, AGYW's age, and family structure. We will collect this information directly from 18 and 19 year-old AGYW.

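### Pilot covariates are chosen by baseline balance tests at about 25 dyads per arm; pre-specifying the baseline score would be a cheap, modest gain for continuous scales

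*Combined protocol and SAP*

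**What the plan says.** The paragraph headed Data Reduction and Analyses begins with a test of the randomisation: "We will check the success of randomization by comparing intervention groups on baseline variables using chi-square tests", with t-tests or Wilcoxon rank-sum tests for continuous variables. The next sentence makes model content depend on the result: "In subsequent analyses, we will control for predictor variables that are not balanced across arms at baseline". No cut-off, outcome model or pre-specified covariate is given. The same paragraph places these analyses in the pilot: "We will conduct analyses on individual outcome indicators and on composite scores comprised of multiple indicators for the pilot study in aim 2".

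The aim 2 procedures give the size: "Approximately 25 dyads will be randomly assigned to the health promotion group and ~25 dyads to IMARA". They also say that randomisation follows the baseline assessment, and that "We will re-interview AGYW and FC 6- and 12-months after baseline for preliminary evidence of feasibility and acceptability".

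Under Data Collection Procedures, "The 6- and 12-month surveys may be administered either in person or via telephone", and "Participants may be asked only a subset of interview questions, depending on time and availability". The Predictors and Mediators text gives AGYW the YSR below age 18 and the ASR from 18.

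Section 3 adds: "Participants in phase 1 (theater testing, pilot test) will be excluded from phase 2".

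**The concern.** When allocation is random, a baseline difference between arms is a chance event, and a significance test of it says nothing about whether the variable predicts the outcome. Precision comes from the correlation between covariate and outcome, and the rule ignores this. It also leaves the model unknown until the data have been seen.

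For a scale measured at baseline and again at follow-up, the strongest covariate is often the baseline value of the same scale. The plan neither prescribes nor excludes adjusting for it routinely; as written, it would enter only if flagged as unbalanced. At stake is some precision in the pilot's exploratory between-arm comparisons of continuous scale scores, and nothing beyond that.

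**Working it through.** The plan gives no alpha, power, SD or correlation for the pilot, so it has no figure of its own to reproduce.

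**Inputs from the documents**
- n = 25 per arm (about 50 dyads split equally).
- n = 20 per arm if retention is at the 80% milestone (0.8 × 25).
- Baseline scores are taken before randomisation; follow-up is at 6 and 12 months.

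**Assumptions**
- Two-sided 0.05 for balance and outcome tests. Reading an unbalanced variable as one with a significant balance test is an inference from adjacent sentences, but no other criterion is offered.
- Normal scores with SD 1 and independent participants.
- Baseline to follow-up correlation r = 0.1, 0.3, 0.5 or 0.7.
- A follow-up-only comparison when the baseline score is not flagged.

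**Step 1: what the balance test can flag.** Smallest significant observed gap = t(0.975, 2n-2) × sqrt(2/n). This is 0.57 SD at 25 per arm, 0.64 at 20 and 0.75 at 15. Under correct randomisation a given score is flagged in 5% of trials by construction. The chance that at least one of k independent variables is flagged is 1 - 0.95^k: 23%, 40% and 64% for k = 5, 10 and 20.

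**Step 2: expected effect of always adjusting.** Relative to an unadjusted follow-up difference, the variance factor is (1 - r²)(1 + 1/(N-4)) with N = 50. The standard error ratios are 1.006, 0.964, 0.875 and 0.722. For change scores the ratio is sqrt(2(1 - r)): 1.342, 1.183, 1.000 and 0.775.

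**Step 3: simulation of the rule itself** (100,000 null trials per cell, 25 per arm; half-widths in SD):

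| | r = 0.1 | 0.3 | 0.5 | 0.7 |
|---|---|---|---|---|
| Half-width, test then adjust | 0.567 | 0.566 | 0.564 | 0.559 |
| Half-width, change score | 0.759 | 0.670 | 0.566 | 0.438 |
| Half-width, baseline always in model | 0.569 | 0.546 | 0.495 | 0.408 |
| Always adjust against the rule | +0.3% | -3.6% | -12.1% | -27.0% |
| Null rejection, rule | 4.9% | 4.7% | 4.3% | 3.6% |
| Null rejection, always adjust | 4.9% | 5.0% | 5.0% | 5.0% |

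Against the better alternative in each column the gain is 0, 4, 12 and 7%. The last figure is (0.438 - 0.408)/0.438.

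**Step 4: smaller samples and skewed scores.**
- At 20 per arm the half-widths are 0.638, 0.637, 0.634, 0.629 (rule) and 0.642, 0.616, 0.559, 0.460 (always adjust), a change of +0.6, -3.3, -11.8 and -26.9%.
- At 15 per arm, an assumed case of scales skipped at follow-up, they are 0.745, 0.744, 0.740, 0.735 and 0.753, 0.722, 0.655, 0.540: +1.1, -3.0, -11.5 and -26.5%.
- For an assumed skewed 0 to 9 score at 25 per arm the change is +0.4, -3.1, -10.6 and -23.6%.

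**Step 5: correlation within session groups.** The intervention is delivered in groups. With an assumed ICC of 0.05, groups of 7 and grouping ignored (40,000 trials), null rejection is 8.4, 8.1, 7.6 and 7.2% under the rule, and 8.4, 8.5, 9.3 and 11.3% with baseline adjustment. A repeat run of the same setting at r = 0.7 gave an actual SD of the estimate of 0.302 under the rule and 0.255 with adjustment. That is 1 - 0.255/0.302 = 16% lower, while the nominal interval narrows by about 26%.

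**The case against.** The strongest case against the point has four parts.

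**Error rates.** A reader might infer that the rule inflates false positives. It does not: overall null rejection is 3.6 to 4.9%. Higher rates appear only in a subset defined after the fact. In the roughly 11% of randomisations with an unflagged gap above 0.4 SD, an unadjusted comparison rejects a true null 5, 7, 9 and 12% of the time at the four correlations, against about 5% with adjustment. That conditional result is no evidence of overall inflation.

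**The comparator.** A reader might also infer that the plan rules out baseline adjustment and so forfeits up to 27% of interval width. The documents name no outcome model, so the follow-up-only comparator is an assumption, as is every correlation. This objection stands, which is why the gain over the better of two alternatives is also given.

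**Relevance.** The listed expected outcomes are risk behaviours, PrEP uptake and HIV/STI incidence, and the move to phase 2 rests on milestones. The follow-up interviews serve feasibility and acceptability, and pilot participants do not enter phase 2. This stands and limits the point to exploratory scales. Telephone mode may lower r. Skipped scales, or a move from the YSR to the ASR at 18, remove the matching score altogether.

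**Clustering.** Under the assumed ICC, adjustment makes the stated error rate more sensitive to ignored grouping, most of all where the nominal gain is largest. This stands, so the change cannot be called free. It does not reverse the conclusion, because the estimate itself is still more precise for r of 0.3 or more.

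**Conclusion.** The point holds as an optional, cheap improvement. Selecting covariates by balance tests lets chance decide the model and captures almost none of the precision available from baseline scores. Always adjusting changes interval half-width by about 0, -4, -12 and -27% at r = 0.1, 0.3, 0.5 and 0.7 against the rule with a follow-up-only fallback.

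These sizes rest on a 0.05 cut-off, independent participants and assumed correlations. They apply only to continuous scores measured with the same instrument at baseline and follow-up. With an ICC of 0.05 ignored, null rejection is about 7 to 8% under the rule and 8 to 11% with adjustment, so part of the apparent narrowing is under-coverage. The documents do not support reading this as a threat to the milestones, the binary or count outcomes, or the phase 2 trial.

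**What to change.** In Data Reduction and Analyses:
- Report baseline data by arm descriptively, and do not use balance tests to select covariates.
- For each continuous scale score measured with the same instrument at baseline and follow-up, pre-specify a linear model with arm and the baseline value of that score, whatever the observed balance.
- State beside these results that the interval ignores any correlation within session groups, and interpret it accordingly.
- If a sensitivity model with further covariates is wanted, name them in advance on prognostic grounds.

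No gain is claimed for the binary or count outcomes. The cost is wording only, since the scores are already collected. The downside is one degree of freedom (about 0.3% wider at r = 0.1) and the greater sensitivity to ignored clustering described above.
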